surgical procedures canceled after randomization, patients who withdrew their consent. The as-treated population is defined by the treatment that was actually received during the trial. This takes into account any deviations from the initially assigned treatment regimen, such as crossovers to the other treatments. The Per-Protocol (PP) population consists of all patients who received the assigned treatment without significant deviations from the protocol. Specifically, the analysis will be restricted to those who completed the full-term intervention as it was initially assigned. Participants with treatment interruptions will be excluded from the PP analysis. The exclusion list will be verified by the steering committee prior to lock of the database. Analyses conducted on these dataset will be treated as supplementary analyses.

General analysis Principles

The COIN trial is designed to assess the impact of preoperative colloid infusion on the occurrence of postoperative complications in surgical patients undergoing non-cardiac surgery with general anesthesia. The estimand is the difference in the incidence of postoperative complications as defined by higher than grade I Clavien-Dindo classification at 30 days after surgery between Colloid bolus administration versus crystalloid bolus administration, in patients undergo elective non-cardiac surgery under general anesthesia. The target population is patients experienced surgery procedure. The patients have the planned surgery canceled after randomization will be excluded from the

primary analyses.

In general, categorical variables are to be compared using χ^2 test or Fisher's exact test. Continuous variables will be compared via t-test or Wilcoxon's rank-sum test. Variable normality will be assessed either via the Shapiro-Wilk test or QQ-plots and residual plots. Variable transformation such as natural logarithm or square root will be applied where necessary, or non-parametric methods (such as Wilcoxon rank sum test) shall be applied.

For the analyses of primary, secondary outcomes, and the process measures, the following information will be presented:

- 📅 The number of patients included in each analysis, by treatment arm
- 📅 A summary statistic of the outcome (such as, number (%), mean (sd), media (IQR), etc), by treatment arm
- 📅 The estimated treatment effect
- 📅 A 95% confidence interval for the estimated treatment effect
- 📅 A two-sided P value

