For all analyses, a significance level of 5% will be used. Multiple comparisons will be conducted without Type I error correction and will be interpreted as exploratory.

Data Presentation and Baseline characteristics

Baseline characteristics will be summarized using descriptive statistics for whole patients cohort and for each treatment group by mean and standard

deviation or median and interquartile range for continuous variables, and the number, frequencies, and percent for categorical variables.

Durations According to Dates

For the indexed surgery, the date of randomization or admission to the intensive care unit corresponding to the surgery date will serve as day 1.

Take, for example, the calculation of the postoperative hospital stay (in days).

The formula is: (Discharge date from hospital - Date of index surgery) + 1

Exact dates will be tracked and documented.

Analysis of the primary endpoints

The primary endpoint, incidence of postoperative complications as defined by higher than grade I Clavien-Dindo classification at 30 days after surgery will be analyzed using Chi-squared test as crude analysis. Unadjusted risk ratios with 95% confidence intervals will be estimated by two-by-two table with the use of log-Normal approximation or other approximation/numeric methods as appropriate. The effect size will be expressed as risk differences (95% confidence intervals) will be estimated using Wald's likelihood ratio approximation test or other methods appropriate, with the number needed to treat as the reciprocal of the risk difference, rounded to the nearest integer.

Secondary Analyses of the primary endpoint

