To account for potential confounders, the adjusted analysis of primary endpoint will use a logistic regression model, where the primary endpoint as the dependent variable and independent variables to include study group (colloid fluid bolus group vs crystalloid fluid bolus group), adjusting for the relevant confounders (planned surgical procedure complexity grade, ASA grade, gender, age, baseline hemoglobin, and baseline creatinine, NPO duration, fluid administration within 12 hours prior to surgery). Odds ratios (95% confidence intervals) will be reported; for those ORs may potentially be biased approximation for RRs, estimates will be obtained via either binomial regressions or converted using bootstrap methods. We will also develop a logistic regression model accounting for the above variables plus any baseline characteristics that appear on visual review to be potentially imbalanced between the study groups.

To account for the center effects, we will fit a mix-effect model with the primary outcome as dependent variable, including group assignment as a fixed effect and participant center (stratification variable) as a random effect. Potential confounders that included in the model are the same as the logistic regression model. Alternative method to use if mixed-effect models fail to reach convergence:

- Include participant sites as a fixed-effect instead of random effect.
- Remove the fixed effect for participant sites
- Adjust for age, hemoglobin, creatinine, fasting duration, etc as a single

continuous variable.

- Remove the covariates in prespecified order to see if convergence reached: gender, hemoglobin, creatinine, age, surgical complexity, ASA grade.

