In addition, we will perform exploratory analyses for additional effect modifiers that are collected after randomization and have the theoretical potential to be affected by the study group assignment:

- Surgical incision type (open, mini-invasive with endoscopy, endoscopic converted to open)
- Choice of sedatives (etomidate, ketamine, propofol, other).
- Use of vasopressor (yes/no)
- Post-induction hypotension (yes/no)
- SBP after fluid bolus infusion (continuous variable)

Handling of Missing Data

Considering the prospective feature of RCT studies and primary endpoints are short-term outcomes, we anticipate no missing primary outcomes and very rare missing values in other variables if any. All demographics and chronic medical history will be filled on site. Intraoperative data will be monitored and documented during surgeries in the operating rooms. Postoperative follow-ups

will be tracked from the electronic health records until discharge of hospital. Other 30-day follow-up data will be obtained via phone-calls, social media software, or updated medical records from any other medical units where available by trained CRCs. Therefore, missing data will not be imputed for the primary or secondary outcome. In adjusted analyses, missing data for covariates will be imputed by multiple imputation. We will combine estimates of the treatment effect and standard errors from the 10 imputed data sets on the log odds scale using Rubin's rules.

Outliers will be subject to confirmation queries to the investigators. In case of confirmation, no modifications will be made before taken into account during analyses.

Corrections for Multiple Testing

We will conduct a single primary analysis of a single primary outcome. Additional analyses are deemed exploratory and hypothesis-generating. No correction for multiple comparisons will be performed.

Table 1 Clavien-Dindo classification

Grade	Definition
Grade I	Any deviation from the normal postoperative course without the need for pharmacological treatment, or surgical, endoscopic, and radiological interventions.

Grade	Definition
	Allowed therapeutic regimens are: drugs as antiemetics, antipyretics, analgetics, diuretics and electrolytes, and physiotherapy. This grade also includes wound infections opened at the bedside
Grade II	Requiring pharmacological treatment with drugs other than such allowed for grade I complications. Blood transfusions and total parenteral nutrition are also included

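### The estimand is a risk difference, but no adjusted risk difference is planned, and the route to an adjusted risk ratio is left open

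*SAP*

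**What the plan says.** - SAP, *General analysis Principles*: "The estimand is the difference in the incidence of postoperative complications" between the two fluids.
- SAP, *Analysis of the primary endpoints*: an unadjusted risk ratio with a 95% confidence interval is planned. For the effect size, "The effect size will be expressed as risk differences", with the number needed to treat (NNT) as the reciprocal.
- SAP, *Secondary Analyses of the primary endpoint*: "the adjusted analysis of primary endpoint will use a logistic regression model" with eight named covariates, and "Odds ratios (95% confidence intervals) will be reported". The only other scale mentioned is the risk ratio: "for those ORs may potentially be biased approximation for RRs, estimates will be obtained via either binomial regressions or converted using bootstrap methods". A second logistic model adds covariates that look imbalanced. A mixed model adds centre as a random effect, with no link or effect measure named.
- SAP, *Handling of Missing Data*: treatment effects are combined with "standard errors from the 10 imputed data sets on the log odds scale" by Rubin's rules.

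The convergence fallbacks listed in the SAP belong to the mixed model. None is given for the binomial regression.

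**The concern.** The adjusted analyses are there to show whether the crude result survives adjustment for prognostic factors and centre. That is easiest to judge when both results are on the scale of the estimand. As planned, the reader gets a crude risk difference and NNT, and then an adjusted odds ratio.

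With about 30% events, an odds ratio adjusted for prognostic covariates lies further from 1 than the crude odds ratio even when the arms are perfectly balanced. A reader could take that shift for a strengthened effect when adjustment has changed nothing.

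The SAP sees part of this problem and offers a risk ratio, but it does not fix how to get one. It names no link, no conversion formula, no rule for choosing between the two routes, and no fallback if the binomial fit fails. The adjusted risk ratio could therefore be settled after the data are seen.

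**Working it through.** **Inputs.** From SAP *Sample Sizes*: 33% v 26%, 90% power, 5% type I error, 10% drop-out, 1010 per arm. After drop-out, 1010 × 0.9 = 909 per arm. The same sentence calls the difference 13%, but 33% − 26% = 7 points, and 7 points is used here. Covariate strengths are not in the SAP and are assumed.

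**The plan's own figure.** The pooled two-proportion formula gives 890 per arm. 890 / 0.9 = 989 per arm, or 1978 in total. With continuity correction it gives 919 per arm, and 919 × 1.1 = 1011 per arm, or 2022 in total. Both are close to 2020, so 33% v 26% is the right pair of risks. Power at 909 per arm is 90.6%.

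**The design effect on each scale.**
- Risk difference: 0.26 − 0.33 = −0.07 (NNT 1/0.07 = 14.3, rounded to 14)
- Risk ratio: 0.26/0.33 = 0.788
- Crude odds ratio: (0.26/0.74)/(0.33/0.67) = 0.713

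**What is planned on each scale.**

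| Analysis | Risk difference | Risk ratio | Odds ratio |
|---|---|---|---|
| Crude primary | yes, with NNT | yes | no |
| Adjusted logistic | no | by an open route | yes |
| Logistic with added covariates | no | not stated | implied |
| Mixed model with centre | no | not stated | implied by log-odds pooling |

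**Simulation.** 300 trials of 909 per arm were drawn from a logistic truth set to marginal risks of 33% and 26%. The eight listed covariates were included: complexity in four levels, ASA in three, sex, four continuous variables and prior fluid. Three covariate strengths were assumed. The plug-in conversion is RR = OR / (1 − p0 + p0 × OR), with p0 the crude control risk.

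| | Weak | Moderate | Strong |
|---|---|---|---|
| AUC | 0.58 | 0.67 | 0.75 |
| True conditional OR | 0.710 | 0.692 | 0.664 |
| Mean adjusted OR | 0.708 | 0.690 | 0.666 |
| Plug-in RR (true 0.788) | 0.783 | 0.768 | 0.748 |
| Log-binomial failure, plain IRLS | 0.7% | 86% | 99.7% |
| Standardised RR | 0.787 | 0.787 | 0.791 |
| Standardised RD, points | −7.0 | −7.0 | −6.9 |
| Crude RD, points | −7.0 | −7.0 | −6.9 |
| Empirical SE, standardised v crude RD, points | 2.24 v 2.21 | 2.07 v 2.16 | 1.82 v 1.91 |

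*Reading the odds ratio.* The true conditional value moves from 0.713 to as low as 0.664 with no imbalance at all. This is non-collapsibility, not removal of confounding.

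*Reading the conversion.* The formula is exact for the crude odds ratio: 0.713 / (0.67 + 0.33 × 0.713) = 0.788. With an adjusted odds ratio it is not: 0.690 / (0.67 + 0.33 × 0.690) = 0.769, in line with the simulated 0.768. The SE of the log risk ratio is √(0.67/(909 × 0.33) + 0.74/(909 × 0.26)) = 0.073. The shifts are therefore ln(0.783/0.788), ln(0.768/0.788) and ln(0.748/0.788) over 0.073, or about 0.1, 0.4 and 0.7 SE.

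*Reading the precision.* The variance ratios are (2.24/2.21)² = 1.03, (2.07/2.16)² = 0.92 and (1.82/1.91)² = 0.91.

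**A second simulation** used 800 trials per scenario (300 for the log-binomial fit, with step-halving) and c-statistics of 0.63, 0.69, 0.74 and 0.80.
- Adjusted OR: 0.70, 0.69, 0.67, 0.63
- Plug-in RR: 0.78, 0.77, 0.75, 0.72
- Log-binomial failure: 1%, 29%, 87%, 99%
- Standardised RD: −0.070, with variance 6%, 12%, 14% and 23% below the crude RD

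The failure rates at similar discrimination (29% at 0.69, 86% at 0.67) show how far they depend on the fitting algorithm and the assumed covariates.

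**The case against.** The strongest reply is that the estimand is estimated. The crude primary analysis gives the risk difference, its interval and the NNT. *Corrections for Multiple Testing* makes that the single primary analysis and everything else exploratory. A secondary adjusted analysis need not use the primary summary measure, and an adjusted odds ratio beside a crude risk difference is common practice. All of this stands. It limits the point to the secondary analyses.

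Four stronger readings are tempting, and the SAP does not support them:

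- *That adjusted and crude results share no scale.* The crude analysis includes a risk ratio, so an adjusted risk ratio would have a like-for-like comparator. What is missing is a defined way to obtain it, and any adjusted counterpart to the risk difference and NNT.
- *That every adjusted result is an odds ratio or is derived from one.* Binomial regression estimates the risk ratio directly. The mixed model's effect measure is not stated; an odds ratio is only implied by the log-odds pooling.
- *That the conversion is biased.* The plug-in formula is not in the SAP. Conversion by bootstrap could equally mean standardised risks with bootstrap intervals, which showed no material bias here. The fair criticism is ambiguity.
- *That the binomial fit will fail.* Failure ranged from about 1% to nearly all trials, depending on covariate strength and algorithm, and the SAP offers the conversion as an alternative route.

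Pooling on the log-odds scale is also right for the odds ratios that the SAP reports. It simply does not serve a risk difference.

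**Conclusion.** The point holds as a gap in the secondary analyses, not as a flaw in the primary one. The estimand, the effect size and the NNT are on the risk-difference scale, and the crude analysis delivers them. No adjusted risk difference is planned, and the adjusted risk ratio has two loosely stated routes.

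The sizes rest on assumed covariate strengths. The adjusted odds ratio would lie between just under 0.713 and about 0.63. A plug-in conversion, if used, would overstate benefit by about 0.5 to 7 points of relative risk (0.783 to 0.72 against 0.788), mostly within one SE. Log-binomial convergence could be a trivial or a serious problem. Standardisation would give the adjusted risk difference without material bias. Its variance would be roughly 0 to 20% below crude; the simulations ran from no gain to 23%, and the SEs from 300 replicates are themselves imprecise.

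The primary test, the sample size and the crude estimate are unaffected.

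**What to change.** Replace the conversion sentence in *Secondary Analyses of the primary endpoint* with text such as:

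> From the prespecified logistic model, and from the model including centre, the risk under each fluid will be standardised over all analysed patients (marginal standardisation). The adjusted risk difference and risk ratio will be reported with 95% confidence intervals by the delta method or bootstrap, with the odds ratio as a supplement.

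Name one of the two interval methods, and state the link of the centre model.

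In *Handling of Missing Data*, add that with imputed covariates the risk difference and log risk ratio are computed in each of the 10 imputed data sets and pooled by Rubin's rules on those scales. Log-odds pooling stays for the supplementary odds ratio.

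The cost is SAP wording and a few lines of code, with the same data, model and covariates. The change should be made before any unblinded final analysis.

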Anesthetic intervention 3) Anesthesia maintenance: using intravenous, volatile or Combined anesthetics for maintenance 5)
Multimodal analgesia: if no contraindications, give non-steroidal anti-inflammatory drugs 15 to 20 min before incision; Local incision infiltration or nerve block. Patient-controlled intravenous analgesia (PCA) was performed as required.
- ◆ Updated Blinding; The intervention fluid will be provided by the coordinating center and will be covered with a opaque bag.

ABSTRACT

Background

This a priori statistical analysis plan describes the relevant statistical considerations and analyzing methods for Colloid infusion for Optimal outcomes In Non-cardiac surgery (COIN) Trial.

Methods:

COIN trial aims to investigate whether the preoperative bolus administration of colloid before the induction of anesthesia reduces the postoperative complications of patients undergo non-cardiac surgery with general anaesthesia comparing to crystalloid bolus administration. The study is a parallel group, blinded, prospective, randomized controlled, multicenter trial. In total, 2020 adult (≥ 18 years old) participants scheduled for elective, non-cardiac surgery with ASA grade I-III will be enrolled. Eligible patients will be randomly assigned (at 1:1 allocation ratio) to infuse either colloid (5 ml/kg Hydroxyethyl Starch 130/0.4) or crystalloid (5 ml/kg of multiple electrolyte injection) before anaesthesia induction within 15 min.

The primary endpoint of interest is a composite measure of postoperative complications (defined as Clavien-Dindo Classification $\geq I$) within 30 days after surgery. The trial will determine whether preoperative colloids infusion can reduce postoperative complications within 30 days.

Conclusions:

This document provides a detailed statistical analysis plan for COIN.

Funding:

The trial is funded by the National Natural Science Foundation of China (81970448), the university and hospital foundation for patient outcome improvement (2021LC2202, 2022LC2213 and XJZT21L17), Shenzhen Medical Research Fund (C2401009).

Trial registration:

ClinicalTrials.gov identifier: NCT05728645. Registered on 05, 02, 2023.

Keywords:

Preoperative fluid management; Fluid bolus administration, Postoperative complications; Colloid; Crystalloid; Post-induction Hypotension; Statistical Analysis Plan

BACKGROUND

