In order to detect a 13% absolute reduction (from 33% to 26%) for the primary outcome of postoperative complications of Clavien-Dindo Grade \geq I up to 30 days after surgery (a risk ratio of 0.8), with 90% power and an overall type I error rate of 5%, a total of 2020 patients (1010 per arm) are required, accounting for 10% drop-out rate.

Randomisation procedure

Randomisation will occur after obtaining informed consent from the eligible patients and shortly before the index surgical procedure is due to start (last-minute randomization). Patients will be centrally allocated to treatment arms in a 1:1 ratio by permuted block randomization stratified with participant centers. To enter a patient into the COIN trial, research staff at each participant site will log on to a secure web-based randomization platform of Redcap data

entry system and obtain a unique patient identification number and allocation assignment. This information will be only revealed to the unblinded investigator who prepare the intervention fluids.

Datasets for Analyses

All statistical analyses within this study will be performed following the intention-to-treat principle. This implies that patients will be analysed in accordance with the treatment groups to which they were initially assigned, as depicted in Figure 1. It is expected that there will be either no or very minimal losses to follow-up for primary and secondary outcomes considering the prospective feature. Patients with missing primary outcome data will be excluded from the analysis (complete-case analysis approach). Missing data for baseline covariates to be included in the analysis model will be accounted for using multiple imputation.

Participation of individual patient in the study will be terminated if they (or their trusted person) withdraw consent. However, if the investigator discontinues the patient's participation, either temporarily or permanently, for reasons in the patient's best interest, especially when serious adverse events are suspected to be related to the intervention, the patient will remain in the analysis to uphold the intention-to-treat principle. Their data will continue to be collected until 30 days after surgery, which marks the final follow-up.

Modified Intent-to-Treat (m-ITT) population excludes individuals who had their

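### The extra adjusted model chooses its covariates by how imbalanced they look between arms: an undefined, observer-dependent criterion that should give way to named prognostic covariates (minor)

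*SAP*

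**What the plan says.** The primary analysis is unadjusted: under *Analysis of the primary endpoints*, the endpoint "will be analyzed using Chi-squared test as crude analysis".

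*Secondary Analyses of the primary endpoint* then describes three regression models:

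- **A prespecified logistic model.** Its stated purpose is control of confounding: "To account for potential confounders, the adjusted analysis of primary endpoint will use a logistic regression model". It has eight covariates, "adjusting for the relevant confounders (planned surgical procedure complexity grade, ASA grade, gender, age, baseline hemoglobin, and baseline creatinine, NPO duration" and fluid given in the 12 hours before surgery.
- **An extended logistic model.** It contains the same variables "plus any baseline characteristics that appear on visual review to be potentially imbalanced between the study groups".
- **A mixed model for centre effects.** For its covariates the SAP says: "Potential confounders that included in the model are the same as the logistic regression model".

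Allocation is 1:1 by "permuted block randomization stratified with participant centers" (*Randomisation procedure*). *Randomisation, Allocation, Concealment and Blinding* states that those who analyse data and assess outcomes do not know the group assignments. *Corrections for Multiple Testing* limits the confirmatory claim to one primary analysis of one primary outcome and adds: "Additional analyses are deemed exploratory and hypothesis-generating". The abstract opens with "This a priori statistical analysis plan describes the relevant statistical considerations".

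**The concern.** Allocation is central and concealed. If it works as planned, any baseline difference between the arms arose by chance. A covariate then earns its place in the model by how well it predicts the outcome. A strong predictor is worth including even when it looks balanced, and a variable unrelated to outcome is not worth including however unequal it looks. The visual rule ignores prognostic value and selects on the observed difference alone.

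The rule also has no content that a second analyst could apply. The SAP does not say what is measured, how large a difference counts, which variables are candidates, who decides or when. The pool is wide: *Data Collection and Management* lists demographics, comorbidities, long-term medication, laboratory tests and clinical evaluations at baseline. *Scope of the Analysis plan* promises that the manuscript will follow the SAP strictly, which cannot be checked for this model.

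At stake is reproducibility. Two careful analysts could report different adjusted odds ratios from the same data. Because the odds ratio is non-collapsible, each covariate set also targets a slightly different conditional effect.

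A related ambiguity sits in the next paragraph of the SAP. The mixed model borrows the covariates of the logistic model, but two logistic models have just been described, so the visually chosen set could be read into it.

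**Working it through.** **The plan's own figure.** The SAP gives no figure for this model, so the only one to reproduce is the sample size that sets the precision of a baseline comparison. Inputs from *Sample Sizes*: 33% v 26%, 90% power, 5% type I error (taken as two-sided), 10% drop-out, 1010 per arm.

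- Pooled two-proportion formula, with p̄ = 0.295: n = [1.960·√(2·0.295·0.705) + 1.282·√(0.33·0.67 + 0.26·0.74)]² / 0.07² = 890 per arm.
- With drop-out: 890/0.9 = 989 per arm, 1978 in total, which is 2.1% below the stated 2020 and close enough to count as reproduced.
- Evaluable patients: 1010 × 0.9 = 909 per arm.

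**How often chance alone triggers the rule.** Assumptions not in the SAP: 20 further baseline variables, independent of each other, each judged on its standardised difference.

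- Standard error of a standardised difference under randomisation: √(2/909) = 0.0469.
- Probability that one variable exceeds a cut-off d: p = 2·[1 − Φ(d/0.0469)].
- Probability that at least one of 20 does: 1 − (1 − p)²⁰. Expected number flagged: 20p.

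| Visible if difference exceeds | d/0.0469 | p per variable | Expected flagged | At least one flagged |
|---|---|---|---|---|
| 0.05 | 1.07 | 0.286 | 5.7 | over 99% |
| 0.08 | 1.71 | 0.088 | 1.8 | 84% |
| 0.10 | 2.13 | 0.033 | 0.7 | 49% |
| 0.15 | 3.20 | 0.0014 | 0.03 | 2.7% |
| 0.20 | 4.26 | 0.00002 | under 0.001 | 0.04% |

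For a binary characteristic present in half the patients, 0.08 is 0.08 × 0.5 = 4 percentage points and 0.15 is 7.5 points. The result therefore runs from almost always to almost never, depending on what the reader of the table notices.

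The number of candidates matters as well. If a variable is flagged at p<0.10, at least one is flagged in 1 − 0.9¹⁵ = 79% of trials with 15 variables and 1 − 0.9³⁰ = 96% with 30. At p<0.05 the figures are 54% and 79%.

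**What the rule does to inference.** Simulation assumptions: 1818 patients, eight listed covariates each with log odds ratio 0.2 per SD, 15 extra candidates, flagging equivalent to p<0.10, 2000 trials per scenario. About 1.5 covariates are added per trial.

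| | Listed eight | Listed + visual | Listed + prognostic extras named in advance |
|---|---|---|---|
| Power, no extra candidate prognostic | 92.2% | 91.9% | not applicable |
| Power, 3 of 15 prognostic (log odds ratio 0.3 per SD) | 92.4% | 92.7% | 93.6% |
| Type I error, range over both scenarios | 4.5–5.3% | 4.5–5.5% | not tabulated |

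The Monte Carlo standard error of each power figure is about √(0.92·0.08/2000) = 0.6 points, so the visual model's change of −0.3 to +0.4 points cannot be told from zero. If the analyst may also choose which flagged covariates to keep, and reports the most significant version, type I error is 5.0–6.1%.

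A separate simulation of 600 trials per scenario, using the 0.08 cut-off and 20 candidates, found that the estimate moved by about 0.12 standard errors (SD). The significance verdict differed from that of the listed-covariate model in 1.2–1.3% of trials.

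**The case against.** The strongest reply is that nothing important hangs on this model. It is announced as an addition, it replaces neither the unadjusted primary test nor the eight-covariate model, and the SAP calls everything beyond the single primary analysis exploratory. If the adjusted results disagree, the hierarchy already tells the reader that the primary result is the chi-squared test. All of this stands, and it is why the point is minor. The hierarchy does not settle which of two adjusted odds ratios to trust, nor make the second one reproducible.

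Four stronger readings are tempting, and the SAP does not support them:

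- **That covariates will be picked with the arms unmasked or the outcomes in view.** The SAP does not say so, and it states that analysts are blinded. Coded arms can still be compared, however, and masking supplies no threshold.
- **That the rule contradicts the description of the plan as a priori.** Announcing such a model in advance is compatible with an a priori plan. Only its content is left open.
- **That the model gains nothing.** A flagged covariate that is strongly prognostic can add a little precision, and the model can serve as a check against chance imbalance in such a variable. The gain comes from the prognostic value, and naming those variables in advance captures it more reliably.
- **That chance will nearly always add a covariate.** This holds only for a sensitive eye or a long candidate list, as the table of cut-offs shows.

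On the mixed model, the fallback order for non-convergence names six covariates, all from the prespecified list. This favours reading the mixed model as using that list, but the text does not say so.

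**Conclusion.** The point holds as a minor one. The SAP states a selection rule, so this is not mere missing detail. The rule uses the wrong criterion for a randomised trial and leaves the model to the observer's judgement.

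A reader might infer that the trial's conclusion or its type I error is at risk. It is not: the primary test is untouched, a mechanically applied rule stays near 5% in simulation, and even selective use of flagged covariates reaches only about 6%.

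The flagging frequencies rest on the assumed number of candidates, their independence and the assumed cut-off. The power figures rest on the assumed prognostic strengths. The argument about the selection criterion needs none of these assumptions.

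**What to change.** Before unblinding, amend *Secondary Analyses of the primary endpoint* in one of two ways:

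1. Replace the visual-review rule with extra covariates named now on prognostic grounds, taken from baseline variables already in *Subgroup analyses*: for example NSQIP complication risk, BMI, baseline SBP and surgical procedure category.
2. Delete the sentence and keep the eight-covariate model as the only adjusted logistic analysis.

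If a model driven by observed imbalance is still run, label it post hoc in the report. In either case, state that the centre-effect mixed model uses the prespecified covariate set.

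The cost is a few lines of SAP text. The sample size and the primary analysis do not change, and the variables named are ones the plan already uses.
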